10 STATISTICS

10.1 General Procedures

The statistical analysis will be undertaken in collaboration with LB Pharmaceuticals Inc.

A detailed Statistical Analysis Plan (SAP) will be finalized and signed before database lock and before analysis of the study being carried out. Any deviations from the analyses described below will be included in the SAP, which will be included in the clinical study report.

Continuous variables will be summarized by treatment using descriptive statistics (n, mean, median, SD, minimum, and maximum). For categorical variables, frequencies and percentages will be presented by treatment. Baseline is defined as the last observation prior to initiation of study medication. Details of the statistical analyses will be provided in the SAP.

10.2 Sample Size

patients will be randomized in a 3:3:3:1 ratio to placebo, LB-102 50 mg QD, LB-102 75 mg QD, or LB-102 100 mg QD, respectively, with randomized to each of the first 3 arms and to the last one (LB-102 100 mg). This will ensure at least 85% power at a 2-sided 5% significance level to detect a treatment difference on the primary endpoint of 8 between either LB-102 50 mg or 75 mg and placebo QD, assuming a common SD of 18, an overall drop-out rate of 25% and a Hochberg procedure to adjust for multiplicity. The sample size was estimated via Monte Carlo simulations using 10,000 simulated trials.

10.3 Analysis Populations

The following analysis populations are planned:

- Safety Analysis Set: all randomized patients who receive study drug. Analyses based on this population will use the actual treatment received rather than the randomized one.
- Intent-to-treat (ITT) Analysis Set: all randomized patients, irrespective of whether they receive the drug or not.
- Modified Intent-to-treat (mITT) Analysis Set: all randomized patients with at least 1 dose of study drug. This will be the main analysis population for efficacy analysis purposes and patients will be analyzed based on the treatment they were randomized to.
- Per-Protocol (PP) Analysis Set: all patients included in the mITT Analysis Set that do not have a major protocol violation. The PP Analysis Set will be used for supportive analyses of the primary and key secondary efficacy endpoints.

Confidential Page 80 of 102

10.4 Statistical Methods

10.4.1 Protocol Deviations

All protocol deviations (PDs) will be assessed and documented on a case-by-case basis before database lock. PDs should be collected by site and grouped into different categories, such as:

- Those who entered the study even though they did not satisfy the entry criteria;
- Those who developed withdrawal criteria during the study but were not withdrawn;
- Those who received the wrong treatment or incorrect dose;
- Those who received a prohibited concomitant treatment.

PDs that are considered to have an impact on the primary and some secondary efficacy variables, will be considered to be major PDs and will lead to exclusion of the patient from the PP Analysis Set. The deviations that might lead to this exclusion will be detailed in a Protocol Deviation Handling Plan and a full list of such occurrences will be provided in the Appendix 16.2 of the CSR (clinical study report).

10.4.2 Patient Disposition

Details for the reasons and number of the Screening failures will be tabulated. Patient disposition will include the number of patients who enroll in the study and the number and percentage of patients included in each analysis set by treatment group. The frequency and percentage of patients who withdraw or discontinue from the study, along with the reason for withdrawal or discontinuation, as well as of those who complete the study, will be summarized by treatment group.

In addition, for the PP Analysis Set only, the reason for exclusion from this analysis set will also be tabulated.

10.4.3 Demographic and Baseline Characteristics

Treatment groups will be compared with respect to patient demographics and baseline characteristics using descriptive statistics only. Demographics and Baseline characteristics, including age, sex, race, weight, height, BMI, and disease history (duration, etc.) will be summarized by treatment group for the Safety Analysis Set.

10.4.4 Analysis of Efficacy

10.4.4.1 Estimand

For the definition of the main study estimand, the following intercurrent events (ICEs) have been deemed as relevant:

a) Taking a prohibited medication prior to Week 4

Confidential Page 81 of 102

b) Starting an emergency treatment prior to Week 4

The primary estimand for all the above events will follow the treatment-policy strategy, to estimate the difference in means (population-level summary) between any active dose of LB-102 and placebo (treatment) in adult patients with acute schizophrenia as defined by the inclusion/exclusion criteria (population) for change from Baseline to Week 4 in the PANSS total score (variable) regardless of the occurrence of the above-mentioned ICEs.

10.4.4.2 Primary Efficacy Endpoint

The primary endpoint is the change from Baseline to Week 4 in the PANSS total score. The null and alternative hypothesis for each dose level are as follows:

H₀: the difference in the change from Baseline to Week 4 in the PANSS total score between LB-102 active treatment and placebo is equal to 0;

H₁: the difference in the change from Baseline to Week 4 in the PANSS total score between LB-102 active treatment and placebo is different from 0.

All efficacy endpoints will be analyzed for the mITT Analysis Set, and the primary endpoint will also be analyzed for the PP Analysis Set.

Principal Analysis

In line with the estimand definition, all data collected after the occurrence of an ICE will be included in the primary efficacy analysis. As a primary analysis, all missing data due to study discontinuation for lack of efficacy or drug-related AEs will be imputed assuming a Missing Not At Random (MNAR) mechanism and assuming that after withdrawal the subjects revert to the distribution of the worst PANSS score values observed up to time of discontinuation, whereas missing data due to discontinuation for any other reason, will be imputed under a Missing At Random (MAR) assumption using a Multiple Imputation (MI) approach.

The primary efficacy endpoint (change from Baseline to Week 4 on the PANSS total score) will be analyzed using a Mixed Model for Repeated Measures (MMRM) approach, including site, visit, treatment, and their interaction as categorical covariates and Baseline PANSS as continuous covariates. Within -patient correlation across repeated measures will be accounted for by using an unstructured correlation, or the best fit structure should an unstructured matrix cause convergence issues. The differences between active treatment groups and placebo at Week 4 will be estimated alongside confidence intervals (CIs) and *P* values. The model will be fit separately for each imputed dataset and results pooled using Rubin's rules to derive one treatment effect estimate.

This analysis will be performed for the mITT and repeated for the PP Analysis Set. Should the mITT and ITT differ substantially (e.g., by at least 10%) the primary analysis will be performed for the ITT and the mITT only be regarded as supportive information.

Confidential Page 82 of 102

A strategy for pooling sites enrolling a limited number of patients will be specified in the SAP prior to unblinding, and the derived 'pooled study site' variable used in all relevant statistical analyses.

Sensitivity Analysis

As a sensitivity analysis, missing data that was imputed under a MAR mechanism in the primary analysis will be imputed under a MNAR mechanism using a tipping-point approach to check robustness of the main analysis results. Details of the MI model for this and the main analysis as well as further sensitivity analyses will be provided in the SAP.

The analysis model will be the same as for the primary analysis, with results obtained on each imputed dataset that will be pooled to provide a single measure of treatment effectiveness (alongside 95% CI and *P* values).

Exploratory Analysis

Further exploratory assessments might be performed to investigate heterogeneity of treatment effects across investigational sites, by summarizing the primary endpoint separately by study site. Subgroup Analysis

Subgroups of interest will be defined based on BMI and severity of disease at Baseline (as measured by the PANSS total score). The primary and secondary endpoints will be descriptively analyzed within the relevant subgroup strata.

10.4.4.3 Secondary Efficacy Endpoint(s)

All continuous secondary efficacy variables will be analyzed using similar approaches to what was described for the primary endpoint, using the appropriate Baseline measurement instead of the Baseline PANSS score, without any data imputation.

The secondary efficacy endpoints to analyze in this way are the following:

- Change from Baseline to Week 4 in CGI-S score
- Change from Baseline to Week 4 in PANSS positive subscale score
- Change from Baseline to Week 4 in PANSS negative subscale score
- Change from Baseline to Week 4 in PANSS Marder factor scores

The MMRM model for the above endpoints will allow to estimate the least square (LS) means and their difference between each active dose and placebo alongside their 95% CI and *P* values, which will only be displayed for informative/descriptive purposes (i.e., no multiplicity correction will be implemented).

An additional exploratory endpoint is clinical response, defined as a reduction of ≥20% from Baseline in PANSS total score at Week 4. This will be analyzed consistently with a "composite

Confidential Page 83 of 102

strategy" estimand, where a patient will be considered a responder if the criteria for clinical response are met and none of the ICEs mentioned above has occurred. For the purposes of this endpoint, only study discontinuations related to the treatment (e.g., lack of efficacy, AE related to the underlying condition such as worsening, etc.) will be considered as relevant ICEs and thus contribute to a non-responder status if occurring.

This endpoint will be analyzed using a logistic regression model including treatment and Baseline PANSS score as covariates to estimate the odds ratio of response of any active dose vs placebo.

10.4.4.4 Exploratory Efficacy Endpoint

The Cogstate Computerized Battery of Tests scores will be analyzed using an Analysis of Covariance (ANCOVA) model including site and treatment as categorical covariates and Baseline Cogstate score as continuous covariate. No imputations will be performed for missing data and similar quantities to compare treatments as for the primary analysis model (LS means and their differences across arms) will be presented.

10.4.4.5 Multiplicity

Results from the analysis of the primary endpoint will be adjusted for multiplicity using a standard Hochberg procedure. This approach involves ranking the P values from the smallest (P(1)) to the largest (P(2)) and comparing the larger P value against 0.05 and if this hypothesis is rejected then even the other one is rejected, otherwise the smaller P values is tested against 0.025.

10.4.5 Analysis of Safety

All safety analyses will be performed using the Safety Analysis Set.

10.4.5.1 Extent of Exposure

Extent of exposure will be summarized by treatment as number of drug administrations received and the overall duration of the exposure (from first to last dose) in days.

10.4.5.2 Adverse Events

AEs will be characterized by type, severity, seriousness, and relationship to treatment. AEs will be coded by preferred term and system organ class (SOC) using Medical Dictionary for Regulatory Activities (MedDRA) Version 23.0.

The incidence of TEAEs (number and percent of patients reporting the AE at least once during the study), SAEs, AEs related to study treatment, SAEs related to treatment, and AEs leading to study discontinuation will be summarized by treatment.

A TEAE is defined as any AE that has an onset on or after the dose of study drug, or any pre-existing condition that has worsened on or after the first dose of study drug.

Confidential Page 84 of 102

Any AE commencing after the last dose of study drug plus 14 calendar days will not be considered treatment-emergent.

The incidence of TEAEs and treatment-related AEs will also be summarized by maximum severity and strongest relationship to study drug by MedDRA primary SOC and preferred term. The summary will include the total number and percentage of patients reporting a particular event as well as the total number of events. In counting the number of events reported, a continuous event, i.e., reported more than once and which did not cease, will be counted only once; noncontinuous AEs reported several times by the same patient will be counted as multiple events.

Relative risks for the occurrence of any AE (i.e., at least 1 AE) during the course of the study as well as for each SOC/preferred term will be calculated for each LB-102 dose vs placebo alongside 95% CI and *P* values. For such analysis, a Poisson regression model with a log-link and a robust error variance will be considered, using the binary indicator for the presence of a given SOC/preferred term (or any AE) as response and treatment as the only covariate whose betas will be exponentiated to return the associated relative risk.

10.4.5.3 Electrocardiogram

A list of patients with abnormal 12-lead ECG parameters will be presented. Baseline and change from Baseline in ECG parameters (heart rate, cardiac rhythm, PR interval, QRS interval, QT interval, and QTc interval) will be summarized at each post-Baseline time point.

10.4.5.4 Vital Signs

Summary statistics for absolute vital sign value and the changes from Baseline will be presented by treatment group for each visit.

10.4.5.5 Physical Examination

Physical examination data will be listed only.

10.4.5.6 Clinical Laboratory Tests

Mean changes from Baseline at each post-Baseline time point for each laboratory variable will be presented. In addition, each reading will be classified as below, within, or above normal range, based on ranges supplied by the laboratory used. Shift tables for the Baseline and follow-up measurements will be presented.

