- 15. Patients with uncontrolled hypertension (diastolic blood pressure [DBP] >95 mmHg in any position or systolic blood pressure [SBP] >145 mmHg) or symptomatic hypotension, or orthostatic hypotension defined as a decrease of ≥20 mmHg in SBP or a decrease of ≥10 mmHg in DBP after at least 3 minutes standing compared with the previous supine blood pressure, OR development of symptoms. NOTE: Blood pressure measurements may be repeated once to ensure reproducibility of the exclusionary result(s) before excluding a patient based on the criteria noted above.
- 16. Patients with known ischemic heart disease or any history of myocardial infarction, congestive heart failure (whether controlled or uncontrolled), angioplasty, stenting, or coronary artery bypass surgery.
- 17. Patients with epilepsy or a history of seizures (with the exception of febrile seizure).

Physical and Laboratory Results

- 18. Patients with a positive urine drug screen or a positive blood alcohol test. Detectable levels of marijuana, barbiturates, benzodiazepines or opiates in the drug screen are not exclusionary if, in the Investigator's documented opinion, the patient does not meet DSM-5 criteria for substance abuse or dependence, in the Investigator's documented opinion, the positive test does not signal a clinical condition that would impact the safety of the patient or interpretation of the trial results, and approval was granted by the Medical Monitor prior to treatment.
- 19. Patients with a history of alcohol use disorder, substance use disorder (by DSM-5 criteria) within 12 months of Screening or a positive screen for drugs of abuse at Screening (unless consistent with current prescription for medical condition).
- 20. The following laboratory test results are exclusionary:
 - Platelets $\leq 75,000/\mu L$ or $\leq 75 \times 10^9/L$
 - Hemoglobin $\leq 9 \text{ g/dL or } \leq 90 \text{ g/L}$
 - Neutrophils, absolute $\leq 1000/\mu L$ or $\leq 1 \times 10^9/L$
 - AST >2 × ULN
 - ALT $>2 \times ULN$
 - Creatine phosphokinase >3 × ULN, unless discussed with and approved by the Medical Monitor
 - Creatinine $\geq 2 \text{ mg/dL or } \geq 176.8 \mu\text{mol/L}$
 - Estimated creatinine clearance of <45 mL/min, calculated using the Cockcroft-Gault equation, at Screening

Confidential Page 41 of 102

- HbA1c $\geq 7.0\%$
- Abnormal free T4 (during Screening), unless discussed with and approve by the Medical Monitor (Note: Free T4 will be measured only if the result for TSH is abnormal)

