9.1.4 Clinical Laboratory Changes

Any abnormality in a laboratory value that is new in onset or which has worsened in severity or frequency from the Baseline condition and meets 1 of the following criteria will be recorded on the AE pages of the eCRF:

- Requires therapeutic intervention or diagnostic tests
- Leads to discontinuation of study drug
- Has accompanying or inducing symptoms or signs
- Is judged by the Investigator as clinically significant

Combined elevations of aminotransferases and bilirubin, either serious or nonserious, and whether or not causally related, meeting the criteria of a potential Hy's Law case (total bilirubin level $\geq 2 \times \text{ULN}$) with simultaneously ALT or AST $\geq 3 \times \text{ULN}$) should always be reported to the Sponsor as soon as possible following the procedures outlined in Section 9.2.2 for SAE reporting, with the Investigator's assessment of seriousness, causality, and a detailed narrative.

Confidential Page 74 of 102

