Of the TEAEs definitely related to study drug, there were 11 cases of elevated prolactin (≥100 μg/L; 50 mg QD, N = 3; 10 mg QD, N = 1; 100 mg QD, N = 1; 150 mg QD, N = 1; 50 mg BID, N = 2; 100 mg BID, N = 1; 75 mg BID, N = 2), 4 cases of moderate dystonia (200 mg QD, N = 1; 100 mg BID, N = 2; 75 mg BID, N = 1), and 1 case of mild ECG QTcF prolongation (458 msec, 200 mg LB-102 QD) that were all resolved with either no course of action (prolactin increase and QTcF interval prolongation) or concomitant medications (dystonia). Due to 2 TEAEs in the same SOC (acute dystonic reaction), treatment was halted in all healthy volunteers taking 100 mg LB-102 BID (Cohort 7) and the 2 healthy volunteers in Cohort 7 taking placebo. As a result, the SRC decided to reduce the dose for Cohort 8 to 75 mg LB-102 BID. Additionally, because QTcF interval was fairly prolonged from pre-dose values (20-46 msec) in all healthy volunteers taking 200 mg LB-102 QD (Cohort 4), the dosage for Cohort 5 was reduced to 150 mg LB-102 QD. Of the TEAEs probably or possibly related to study drug, there were 4 cases of nausea (100 mg LB-102 QD, N = 1; 200 mg LB-102, N = 1; 100 mg

Confidential Page 93 of 102

LB-102 BID, N = 1; 75 mg LB-102 BID, N = 1) and 1 case of vomiting (100 mg LB-102 BID), urticaria (100 mg LB-102 QD), gastroesophageal disease (200 mg LB-102), insomnia (75 mg LB-102 BID), dizziness (75 mg LB-102 BID), and somnolence (75 mg LB-102 BID).

Vital signs and physical examination results were largely unchanged from Baseline. Other than increases in prolactin, chemistry laboratory results were also relatively unchanged throughout study treatment. C-SSRS did not change during study treatment.

Pharmacokinetics Results

In Part A (SAD), LB-102 was rapidly absorbed and LB-102 concentration generally declined from peak in an apparent biphasic manner. The estimates of mean t_½ of LB-102 generally ranged from 11.993 to 14.146 hours; exposure (as measured by C_{max}, AUC_{0-t}, and AUC_{0-inf}) increased in a slightly greater than dose-proportional manner. Mean C_{max} ranged from 24.1 ng/mL at the lowest dose of 10 mg LB-102 to 975.667 ng/mL at the highest dose of 200 mg LB-102. Mean AUC_{0-t} ranged from 221.911 h•ng/mL at the lowest dose to 6709.821 h•ng/mL at the highest dose. Mean AUC_{0-inf} ranged from 252.637 h•ng/mL at the lowest dose to 7002.109 h•ng/mL at the highest dose. Apparent clearance (CL/F) appeared to decrease as dose increased (42.44 L/h to 28.89 L/h).

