### 5.13.2 Laboratory Data

Descriptive statistics of the observed values and change from baseline (continuous data) will be presented by treatment group and visit for each hematology, urinalysis, chemistry, coagulation, and hormone (ACTH, TSH, cortisol) parameter. Each measurement (continuous data) will be classed as below, within, or above normal range, based on ranges supplied by the laboratory used. Shift tables in relation to the normal range from baseline to each follow-up visit will be presented.

A summary of the number of abnormal parameter values will also be provided. All laboratory data will be listed, with a separate listing only including abnormal (i.e. out of range) values.

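### Laboratory shift tables stop at above normal, so worsening from a raised Baseline shows as no shift, and no planned table counts patients by arm by size of elevation or by the potential Hy's Law definition.

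*Protocol*

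**What the plan says.** The grading rule is the same in both documents. Protocol 10.4.5.6: "In addition, each reading will be classified as below, within, or above normal range, based on ranges supplied by the laboratory used". SAP 5.13.2: "Each measurement (continuous data) will be classed as below, within, or above normal range, based on ranges supplied by the laboratory used". The SAP then states: "Shift tables in relation to the normal range from baseline to each follow-up visit will be presented".

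SAP 5.13.2 also plans:
- a continuous summary: "Descriptive statistics of the observed values and change from baseline (continuous data) will be presented by treatment group and visit". Under SAP 5.3 this means n, mean, median, SD, minimum and maximum;
- a count: "A summary of the number of abnormal parameter values will also be provided". For the separate listing of abnormal results, the same paragraph explains abnormal as out of range;
- a listing of all laboratory data.

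For entry, exclusion 20 (protocol 5.2) rules out ALT or AST only when above 2×ULN. Its CPK limit is "Creatine phosphokinase >3 × ULN, unless discussed with and approved by the Medical Monitor".

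For on-study values, protocol 9.1.4 defines a potential Hy's Law case as total bilirubin at or above 2×ULN with simultaneous ALT or AST at or above 3×ULN. It sends "Combined elevations of aminotransferases and bilirubin, either serious or nonserious, and whether or not causally related" that meet this definition to the sponsor by the serious adverse event procedure.

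Prolactin is part of the serum chemistry panel and is named within the safety endpoints (protocol 3.4, SAP 2.2.4). The Phase 1 summary in protocol 14.2.1 reports that "there were 11 cases of elevated prolactin", defined there as 100 µg/L or more.

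**The concern.** A shift table is meant to show, arm by arm, how many patients moved to a worse class than the one they started in. That works only if there is a worse class to move to. Here the eligibility rules let patients start in the top class for ALT, AST and CPK, and for them the table cannot register any deterioration. For patients who start within normal it registers that a limit was crossed but not by how much.

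Protocol 9.1.4 itself treats the size of an elevation as important, because it names multiples of ULN that trigger expedited reporting. The SAP does not carry that definition into any output: it mentions neither Hy's Law nor a multiple of ULN. At stake is the categorical comparison between arms on a stated safety endpoint.

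**Working it through.** There is no sample size or power figure to reproduce on this point. The check applies the stated rule to example values and then looks for any other planned output that would supply the missing count.

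**1. Classification.** Let b be the Baseline value and f the follow-up value, both in multiples of ULN. The class is above if the value exceeds 1; otherwise, for the values used here, it is within. A shift is recorded only if class(b) differs from class(f). The example values are chosen for illustration. Baselines up to 2.0 lie inside the ALT/AST entry limit.

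| Baseline b | Follow-up f | Cell | Shift shown |
|---|---|---|---|
| 1.2 | 3, 5, 10 | above to above | none (3 of 3) |
| 1.8 | 3, 5, 10 | above to above | none (3 of 3) |
| 2.0 | 3, 5, 10 | above to above | none (3 of 3) |
| 0.8 | 1.1 | within to above | yes |
| 0.8 | 10 | within to above | yes, same cell as 1.1 |

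So 9 of 9 rises from a raised Baseline show nothing, and a trivial and a tenfold result from a normal Baseline cannot be told apart.

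**2. Continuous summaries.** Suppose one patient goes from 2 to 10×ULN and nobody else changes. The arm mean change is (10 − 2)/n = 8/n. Arm sizes are blacked out, so n is assumed:
- n = 80: 8/80 = 0.10×ULN
- n = 107: 8/107 = 0.075×ULN
- n = 140: 8/140 = 0.057×ULN

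The middle value is plausible. With the plan's difference of 8, SD of 18 and 25% drop-out, simulated Hochberg power for at least one dose is 84.2% at 75 evaluable per arm (75/0.75 = 100 randomized) and 86.5% at 80 (80/0.75 ≈ 107). The 100 mg arm is one third as large under 3:3:3:1, so there the figure would be about 8/(107/3) = 0.22×ULN. The maximum would show this patient, but it does not say whether one patient or several reached a high value.

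**3. Table list.** In SAP Section 10 the laboratory tables are 14.3.4 (abnormal values) and 14.3.7.1 to 14.3.7.7 (hematology, chemistry, urinalysis, coagulation, hormones, with shift tables for hematology and chemistry). No title refers to a multiple of ULN or to Hy's Law, and SAP 5.13.2 gives no such cut-off for any of them.

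**4. Prolactin.** The Phase 1 cases at or above 100 µg/L add up: 3 + 1 + 1 + 1 + 2 + 1 + 2 = 11, among 8 cohorts × 6 active = 48 dosed volunteers (11/48 = 22.9%; Clopper-Pearson 95% CI 12.0 to 37.3%). That cut-point was used in Phase 1. No planned table in this study counts patients reaching it.

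**The case against.** The strongest reply is that large elevations will not go unseen. The minimum and maximum of value and change are tabulated by arm and visit, out-of-range values are summarized and listed, and protocol 9.1.4 requires new or worsened abnormalities to be recorded as adverse events when they need intervention or tests, lead to discontinuation, have symptoms, or are judged clinically significant. Those events are then tabulated by arm and preferred term, with a relative risk for each dose against placebo (SAP 5.13.1). Potential Hy's Law cases reach the sponsor individually with a narrative. The table shells and the safety review committee's data outline are separate documents and may contain more.

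All of this stands, and it rules out one tempting inference: that the protocol's thresholds are counted nowhere. What can be said is narrower. The adverse event route yields preferred terms, partly on investigator judgement, and the other outputs give extremes, out-of-range counts or individual values. None is a planned count of patients by arm at a stated size of elevation.

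A reader might also infer that the three classes will fail to separate the doses on prolactin while a higher cut-point would succeed. The documents do not support that. The Phase 1 once-daily cases at or above 100 µg/L were 1, 3, 1, 1 and none listed at 10, 50, 100, 150 and 200 mg, with 6 active volunteers each. These are small counts with no rising gradient. Nor can one assume that prolactin at Baseline is still raised by earlier antipsychotics: exclusion 22 requires a washout of at least 5 half-lives, and at least one and a half injection cycles for depot drugs.

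Finally, only the Hy's Law definition is an on-study laboratory threshold. The 2× and 3×ULN limits are entry criteria, and 100 µg/L is a Phase 1 reporting cut-point.

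**Conclusion.** The point holds. It follows from the three-class rule and the entry limits alone, and the SAP repeats the rule without repairing it. Any rise from an above-normal Baseline is invisible in the shift tables, the size of a rise from a normal Baseline is lost, and no planned table counts patients by arm by size of elevation or by the protocol's own Hy's Law definition.

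The practical size cannot be given, because the documents do not say how many patients will enter above normal. The mean-change figures rest on assumed arm sizes. The gap concerns descriptive Phase 2 safety tables; no hypothesis test or efficacy conclusion depends on it. It does not mean that a serious hepatic case would be missed, and it does not show that prolactin would separate the doses under a different cut-point. It is still worth closing, because laboratory safety is a stated endpoint and the remedy is cheap.

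**What to change.** Keep the three-class shift tables. Add to SAP 5.13.2, and to the table list in SAP Section 10, one by-arm table of each patient's worst on-treatment value against that patient's own Baseline class:
- ALT, AST and CPK in multiples of ULN with several upper grades, for example >1 to <3, 3 to <5, 5 to <10 and ≥10×ULN. These cut-points are illustrative. Several grades are needed because a single top class starting at 3×ULN would repeat the problem for a patient admitted with a higher CPK.
- Total bilirubin at or above 2×ULN.
- A row for ALT or AST at or above 3×ULN with total bilirubin at or above 2×ULN, assessed simultaneously as 9.1.4 requires.
- Patients with prolactin at or above 100 µg/L, by arm and sex, labelled as a descriptive cut-point from the Phase 1 report, with no claim that it will separate the doses.

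One inconsistency should be settled at the same time. The schedule of assessments footnote gives the exclusionary CPK value as at or above 3×ULN, while exclusion 20 and Table 14.2 give above 3×ULN. These passages must be reconciled.

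The cost is a paragraph of SAP text and one descriptive table from data already collected. No new assessments are needed, and the significance level and efficacy analyses do not change. A rise that stays inside one grade will still not register, and the top grade remains open-ended, so the maxima and listings should stay.
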